#### 1. Purpose and objectives. *List the purpose and objectives:*

The overarching goal of this pilot prospective randomized controlled study is to compare patient-reported and clinical operations outcomes between in-person genetic counseling (IPGC – control) and telephone-based genetic counseling (TGC – intervention) in an indigent English or Spanish-speaking population seeking genetic counseling for hereditary cancer syndromes to create a framework for effective and efficient genetic service delivery in these populations nationally. General genetic education and principles will be conveyed through a standard genetic counseling session including a pre-test education video in both the TGC and IPGC arms. Our primary project objectives are to compare the following outcomes between the IPGC and TGC study arms. Aim 1: Patient reported outcomes – A. Patient satisfaction with genetic counseling visit; B. Knowledge of basic principles of cancer genetics and implications of genetic testing for personal healthcare and relatives. Secondary objectives for this aim are: 1. Patient ability to make informed choice; and 2. Genetic counseling-specific empowerment outcomes. Aim 2: Clinical outcomes – visit completion rate; Secondary objectives are: 1. Genetic testing completion rate; and 2. Genetic testing cancellation/failure rate. We hypothesize that patients in the TGC arm will not have significant differences in knowledge, satisfaction, informed choice or genetic counseling-specific empowerment compared to the IPGC arm. We also expect significantly increased visit completion rate and lower test completion rate in the TGC arm compared to the IPGC arm, but no significant difference in sample failure rate.

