**Randomization and Scheduling:**

Study coordinator (SC) will monitor referral queue daily

Randomization software (<http://abtesting.ideas42.org/randomize/>) will be used to randomize patients in the referral queue to each study arm (in-person genetic counseling or IPGC/ telephone genetic counseling or TGC). Patients who meet the following exclusion criteria will not be randomized to a study arm. Patients who are excluded from the study will be scheduled for an appointment as per normal clinic protocol by the clinic schedulers.

SC will monitor number of participants per study arm and adjust recruitment accordingly.

Patients who have been randomized to a study arm will be scheduled for IPGC or TGC by schedulers at John Peter Smith (JPS) and Parkland Hospital (PHHS). Schedulers will inform patients of their appointment as per normal clinic protocol. Spanish-speaking patients will be contacted with an interpreter.

Patients who elect alternative service delivery model for genetic counseling than what was assigned after randomization will be excluded from the study. The genetic counseling appointment type will be modified based on patient preference and patient will continue with scheduled visit, but not as part of the study.

SC will record the following data for all referred patients in Research Electronic Data Capture (RedCap), a secure, web-based application for research data: MRN; study arm assigned; genetic counseling appointment date; if patient was excluded from study, and reason for exclusion. The following demographic data will also be tracked: patient's age; patient's sex; patient's race and ethnicity; patient's preferred language; patient's contact information (phone number and e-mail address)

**Study Eligibility Determination and Informed Consent.** One week prior to scheduled genetic counseling appointment, SC will call patient to assess if patient meets study eligibility criteria. Spanish-speaking patients will be contacted with an interpreter.

If SC cannot reach the patient, SC will make second contact attempt the following business day.

Scheduled patients who cannot be reached or do not call back will be excluded from study.

SC will record the following data in RedCap: contact date and outcome; if eligibility criteria were met; if patient was excluded from study, and reason for exclusion.

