If patient qualifies for study, SC will describe study protocol and get verbal consent for study participation using the consent script. All patients will be sent a hard copy of the consent document for their records (available in English and Spanish) electronically along with the study surveys via RedCap.

Patients who decline will be excluded from study. Study participation status will be recorded in RedCap (including reason for declining participation).

Patients who decline to be in the study will be sent an appointment letter and will continue with scheduled genetic counseling appointment as per normal clinic protocol, not as part of the study.

**Pre-Appointment Resources and Survey Completion.** Patients who agree to participate in the study will be sent the pre-appointment survey (Appendix B). A Spanish version of the survey will be sent to Spanish-speaking patients. Surveys will include a hard copy of the consent document that can be downloaded as desired. Survey links will be sent to patients via email. All surveys will be available through REDCap.

The pre-appointment survey will consist of the Multi-dimensional Model of Informed Choice (MMIC) assessment and the Genomics Outcome Scale (GOS).

SC will check pre-appointment survey completion status two business days prior to appointment.

Patients with incomplete pre-appointment surveys will be contacted two business days prior to appointment and will be reminded to complete survey. Patients will be offered the option to complete survey via telephone with SC. Spanish-speaking patients will be contacted with an interpreter.

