## Form A

IRB #	STU -----
-------	-----------

SC will attempt to contact patients who cannot be reached the following business day.

Patients who do not complete pre-appointment survey will be excluded from study but will continue with scheduled genetic counseling appointment as standard of care.

Pre-appointment survey completion status and survey completion method will be recorded in RedCap by SC.

Genetic Counseling and Genetic Testing. Patients who are unable to watch the educational video prior to, or during their genetic counseling visit will be excluded from the study. They will still continue with their appointment, but not through the study. Patients excluded for this reason will be recorded in RedCap by SC.

Sample failure and test completion status will be recorded in RedCap by SC. Failure to complete testing will not exclude patient from the study itself.

Post-Appointment Survey and Study Incentive. SC will send post-appointment survey within 24 hours of GC appointment. A Spanish version of the survey will be sent to Spanish-speaking patients.

The post-appointment survey will consist of the Multi-dimensional Model of Informed Choice (MMIC) assessment, the Genetics Outcome Scale (GOS) and the Genetic Counseling Satisfaction Scale (GCSS).

SC will monitor survey completion status. Those with incomplete post-appointment surveys will receive reminder two business days post-appointment and will be offered option to complete the survey via telephone with SC.

If patient is not reached, SC will attempt to contact patient the following day (three business days post-appointment).

Those with incomplete surveys one week after the genetic counseling appointment will be excluded from study. This data will be recorded in RedCap.

Those who complete study surveys will be sent a \$15 gift card electronically.

Location/Setting. For IPGC, patients will be seen within PHHS/JPS clinics. Spanish translation services are provided through PHHS and JPS for patients in their institutions. TGC patients will not be required to be in a certain environment, but we anticipate they will be in their homes or workplace in a secure, private location. GCs will either be in a HIPPA compliant setting offsite or within a UTSW workspace for TGC visits.

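### Visit completion, a primary outcome, is not exempted from the post-randomisation exclusions, so the arms would not be compared as randomised

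*Combined protocol and SAP*

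**What the plan says.** Under Randomization and Scheduling (section 4.a), software "will be used to randomize patients in the referral queue to each study arm". The eligibility call and verbal consent come later, about one week before the appointment. Six rules then take randomised patients out:

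- **Change of mode** (Randomization and Scheduling): "Patients who elect alternative service delivery model for genetic counseling than what was assigned after randomization will be excluded from the study". The "patient will continue with scheduled visit, but not as part of the study".
- **Not reached** (Study Eligibility Determination and Informed Consent): "Scheduled patients who cannot be reached or do not call back will be excluded from study".
- **Consent refused** (same heading): "Patients who decline will be excluded from study".
- **No pre-visit survey** (Pre-Appointment Resources and Survey Completion): "Patients who do not complete pre-appointment survey will be excluded from study".
- **Video not viewable** before or during the visit (Genetic Counseling and Genetic Testing): excluded.
- **No completed survey one week after the appointment** (Post-Appointment Survey and Study Incentive): excluded.

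The only exemption is for genetic testing: a patient who does not complete testing stays in the study. Nothing similar is written for attendance.

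Data Analysis and Table 1 make visit completion a primary outcome. Table 1 takes it from a database query as completed visits out of scheduled visits, powered at 100 per arm. Section 1 states the hypothesis: "We also expect significantly increased visit completion rate and lower test completion rate in the TGC arm compared to the IPGC arm". No analysis set is defined for any outcome.

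**The concern.** For satisfaction and knowledge, a patient without a survey has no outcome, so some loss is unavoidable. Visit completion is different: it can be known for every scheduled patient, and the loss is created by the rules.

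The rules are unlikely to be neutral. A patient who cannot be reached a week beforehand, or does not complete the pre-visit survey, may also be more likely to miss the visit. Changing mode depends on the assigned arm, because the patient is turning down that arm's mode. Exclusions that are related to attendance and differ by arm undo what randomisation provides.

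At stake is the one primary hypothesis that predicts a difference, tested at 0.05 in a study meant to inform service delivery nationally.

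**Working it through.** **The plan's own figure.** Inputs from the sample-size text and Table 1: 63% control, 81.6% intervention, two-sided 0.05, 80% power, 100 per arm. With mean proportion p̄ = 0.723 and d = 0.186:

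n = [1.96·√(2p̄(1−p̄)) + 0.8416·√(0.63·0.37 + 0.816·0.184)]² / d² = 89.7 per arm.

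With continuity correction, (n/4)·[1 + √(1 + 4/(n·d))]² = 100.1 per arm. The stated 18.6 points is therefore reproduced at 100 per arm (17.7 points uncorrected). The power figure is sound. The question is which patients it describes.

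**One-week survey rule, two readings.**

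1. *Applied to everyone.* Patients who did not attend leave the set, and little or no attendance information remains.
2. *Applied to attenders only.* Attenders without a survey are dropped and non-attenders stay. With attendance p and non-return u among attenders, the observed rate is p(1−u) / [p(1−u) + 1−p]. The documents give no u. The table uses 10% to 40%, with 30% borrowed from the plan's overall dropout figure.

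| u | 63% reads as |
|---|---|
| 10% | 60.5% |
| 20% | 57.7% |
| 30% | 54.4% |
| 40% | 50.5% |

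At 30% the fall is 63.0 − 54.4 = 8.6 points within an arm. The comparison is distorted when u differs by arm. If both arms truly attend at 63%, non-return of 20% in one and 30% in the other gives an apparent difference of 57.7 − 54.4 = 3.3 points.

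**The other exclusions: logical bounds.** If a share s of an arm with attendance p is removed, the remainder lies between (p−s)/(1−s), when all those removed would have attended, and p/(1−s), when none would. With p = 0.63 and assumed shares:

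- s = 10%: 0.53/0.90 = 58.9% to 0.63/0.90 = 70.0%
- s = 20%: 0.43/0.80 = 53.8% to 0.63/0.80 = 78.8%

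**A less extreme illustration.** Suppose true attendance is 63% in both arms and only in-person patients change mode and are removed. With attendance c among those removed, the in-person rate becomes (0.63 − s·c)/(1 − s). The apparent telephone-minus-in-person difference is:

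| s | c = 30% | c = 63% | c = 90% |
|---|---|---|---|
| 10% | −3.7 points | 0 | +3.0 points |
| 20% | −8.3 points | 0 | +6.8 points |

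With 140 randomised per arm and s = 20%, a nominal 5% two-proportion test (normal approximation) would reject a true null about 28% of the time at c = 30% and 19% at c = 90%.

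**Precision in a wider set.** The number randomised is not given. If the 280 enrolled were analysed, 140 per arm, the detectable difference from 63% is 15.9 points continuity-corrected (15.2 uncorrected). Power for 63% against 81.6% is 92.1% corrected (94.0% uncorrected).

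**The case against.** The strongest reply is that Table 1 already separates visit completion from the survey outcomes: it comes from a database query, with scheduled visits as its base. Under Randomization and Scheduling, the "SC will record the following data for all referred patients in Research Electronic Data Capture", including assigned arm, appointment date and reason for exclusion. A reader could infer that every scheduled patient counts in the assigned arm. That reading is possible, but the plan does not commit to it. Table 1 does not say whether excluded patients' visits count, while the text places several of those visits outside the study. The row is powered at 100 per arm, the number expected to complete the surveys. Attendance is not among the items recorded for all referred patients.

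Three other points limit the illustrations:

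- Applying the one-week rule to non-attenders is strained, since it would empty a named primary outcome of meaning.
- Equal non-return in both arms cancels from the odds ratio. At 30%, 63% and 81.6% become 54.4% and 75.6%, and the odds ratio stays at 2.60; the risk difference moves from 18.6 to 21.3 points. If the arms are truly equal, no false difference appears. The 8.6-point shift is therefore not itself a bias in the comparison.
- If those removed attend at the same rate as those kept, there is no bias.

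Finally, because consent follows randomisation, leaving out decliners and unreached patients may be a consent constraint. That affects how complete the repair can be. It does not explain removing consented patients for a missing survey or an unwatched video.

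**Conclusion.** The concern holds and should be settled before analysis. Applied as written, the exclusions break the as-randomised comparison for the only primary outcome expected to differ, and the general sentence on dropouts and missing data in Data Analysis does not restore the removed patients.

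The size and direction of the bias cannot be estimated from the documents, because exclusion rates by arm and attendance among excluded patients are not given. The figures above show what is possible under assumed shares of 10% to 40%; they are not forecasts. The 18.6-point calculation is correct at 100 per arm and conservative if the 280 enrolled are analysed.

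**What to change.** - State that visit completion is analysed in all randomised and scheduled patients by assigned arm, including those who change mode. Limit the contact, survey and video exclusions to the survey outcomes.
- Confirm that the database query returns attendance for these patients.
- If scheduling data of unconsented patients may not be used, analyse all consented patients by assigned arm, including non-attenders, mode changers, survey non-completers and those who could not watch the video. State the remaining selection as a limitation; this set is still not the randomised groups.
- Reconcile 280 enrolled at 1:1, which is 140 per arm, with the 100 enrolled per arm in the same sentence. Restate the visit-completion row of Table 1 at the n of the chosen set.
- Report the numbers randomised and excluded per arm, by reason.

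The cost is analysis-set wording, one restated table row, possibly a wider query, and possibly an IRB clarification. No patients or procedures are added. Counting mode changers in their assigned arm may dilute the difference, which should be borne in mind when the row is restated.

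### Eligibility and consent are settled after the arm is assigned and booked, by a coordinator who records the arm, so the enrolled groups need not be the randomised groups

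*Combined protocol and SAP*

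**What the plan says.** All of this is in section 4.a of the combined protocol and SAP.

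- **Randomization and Scheduling.** The software "will be used to randomize patients in the referral queue to each study arm". The same paragraph states: "Patients who meet the following exclusion criteria will not be randomized to a study arm". Next, "Patients who have been randomized to a study arm will be scheduled for IPGC or TGC by schedulers", and the schedulers tell patients about the appointment in the usual way. A patient who then opts for the other mode of counselling leaves the study but still receives a visit.
- **The coordinator's knowledge of the arm.** For all referred patients the study coordinator records "MRN; study arm assigned; genetic counseling appointment date; if patient was excluded from study, and reason for exclusion". In addition, "SC will monitor number of participants per study arm and adjust recruitment accordingly". No concealment of the arm from the coordinator is described.
- **Study Eligibility Determination and Informed Consent.** The timing of the check is set here: "One week prior to scheduled genetic counseling appointment, SC will call patient to assess if patient meets study eligibility criteria". After a second attempt, "Scheduled patients who cannot be reached or do not call back will be excluded from study". For those reached, "If patient qualifies for study, SC will describe study protocol and get verbal consent for study participation using the consent script". Patients who decline leave the study and keep their scheduled appointment. The reason for exclusion or refusal is recorded.
- **Data Analysis.** The arms are compared by regression and chi-squared tests, with example covariates of age, race, sex and language. No analysis set is defined that retains every randomised patient.

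**The concern.** Randomisation makes two groups comparable at the moment of assignment. Here the study groups are formed later, by a screen and a consent request made when the coordinator has the arm on record and the patient has already been told of the booked visit. Whoever drops out between assignment and consent is lost from the comparison, and nothing in the procedure makes that loss equal in the two arms.

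Satisfaction, knowledge, empowerment and informed choice are all measured on the groups that remain. Visit completion is exposed as well if it is analysed in enrolled patients only, because a patient who answers the telephone and agrees to surveys is plausibly also more likely to attend. The example covariates do not include motivation, transport or digital access, so adjustment for them would not be expected to repair a difference in who entered.

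**Working it through.** **1. The plan's own figures.** Inputs from Data Analysis and Table 1: 0.398 SD, 80% power, two-sided 0.05, 100 per arm. n = 2 × (1.960 + 0.842)² / 0.398² = 15.70 / 0.1584 = 99.1, so 100 per arm. For visit completion, 63% against 81.6% needs 90 per arm without a continuity correction and 101 with one. The stated size reproduces, and the order of steps does not alter it. The question is which patients make up the 100.

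**2. The order of steps.**

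| Step | Arm already assigned? | Who can leave here |
|---|---|---|
| Queue randomisation | Assigned at this step | Patients meeting exclusion criteria, by the stated rule |
| Booking in the assigned mode; patient informed | Yes | Patients who choose the other mode |
| Coordinator's call, one week before the visit | Yes, and recorded by the coordinator | Ineligible; not reached |
| Verbal consent | Yes | Decliners |

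Four routes out follow assignment: ineligible, not reached, declining, and choosing the other mode. For the last, the triggering preference is for telephone in one arm and for in-person in the other, so the exclusion removes different kinds of patient by construction. The 30% allowance in Data Analysis covers survey non-completion after enrolment. Losses between assignment and consent are outside it, and the number to be randomised is not stated.

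**3. Survey outcomes.** Let p be the share of an arm that does not enter and D the mean outcome of entrants minus that of non-entrants. The entrants' mean equals the whole-arm mean plus p × D. The bias in the arm difference is therefore p(TGC) × D(TGC) − p(IPGC) × D(IPGC). It is zero if both quantities are equal across arms. The documents give neither, so no figure follows from them.

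**4. Visit completion, an illustration under assumed inputs.** Suppose there is no true effect and completion is 63% overall (the plan's control rate). The rest is assumed: half the patients are engaged and half less engaged, both halves enter at 80% in one arm, and in the other arm the engaged enter at 80% and the less engaged at a lower rate e. Let H and L be the completion rates of the two halves. Completion among entrants in the second arm = (0.5 × 0.8 × H + 0.5 × e × L) / (0.5 × 0.8 + 0.5 × e). For H = 80%, L = 46%, e = 60%: (0.320 + 0.138) / 0.70 = 65.4%, which is 2.4 points too high. The type I error is that of the two-sided test of proportions with 100 analysed per arm.

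| e | Completion H / L | Spurious difference | Type I error |
|---|---|---|---|
| 80% | either pair | 0 | 5% |
| 60% | 80% / 46% | 2.4 points | 6.5% |
| 60% | 95% / 31% | 4.6 points | 10.4% |
| 40% | 80% / 46% | 5.7 points | 13% |
| 40% | 95% / 31% | 10.7 points | 37% |

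Which arm would be favoured is not known.

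**The case against.** Four arguments on the other side deserve weight.

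- **The two statements on exclusion may be compatible.** A reader might infer that the protocol flatly contradicts itself by screening after it has said that excluded patients are not randomised. The documents do not establish this. The exclusion list is not in the reviewed copy, from which pages were removed, and a chart screen at the queue followed by a telephone check of items only the patient can answer would fit the wording. The single eligibility review in table 4.d does not say when it takes place. What stands is that the text describes no such two-stage screen, so the passages have to be reconciled.
- **Refusal may differ little between arms.** A reader might infer that patients facing a trip and patients awaiting a call are agreeing to different studies. Decliners keep their booked appointment, so refusing does not spare anyone the trip. The research-only items in table 4.d, the eligibility review and the surveys, are the same in both arms. This weakens the refusal route. It does not touch the mode-switch exclusion.
- **Booking lead times are unknown.** One might argue that tying the call to the appointment screens the arms at different times after referral. No lead times are given, and a fixed one-week interval also standardises the gap from call to visit. I make nothing of this.
- **Queue randomisation can be deliberate.** It permits a comparison of attendance in unselected referrals, which suits a study about access, and Table 1 takes visit completion from a database query. That benefit is obtained only if patients are analysed as randomised. The plan instead removes them and gives no such rationale.

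**Conclusion.** The concern holds as a design risk. Eligibility and consent follow assignment, booking and notice of the appointment; the coordinator who makes the call records the arm; and four kinds of patient are then removed, one of them for a reason tied to the arm. The enrolled groups are therefore not the randomised groups, and entry can differ between them.

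That entry will differ is not shown. The size of any bias cannot be computed from the documents, and the 0 to 10.7 points above rest wholly on assumed entry rates and an assumed split of patients. A percentage of the 0.398 SD effect for the survey outcomes would rest on invented inputs and should not be quoted. The exclusion data the plan already collects would let the sponsor see whether entry did differ, but Data Analysis does not commit to reporting them by arm.

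**What to change.** **Preferred.** Make the existing eligibility-and-consent call when the patient enters the referral queue, before the randomisation tool is run. Randomise only those who qualify and consent, and keep the later contact for the pre-appointment survey. Amend the two paragraphs of section 4.a to match, and state which criteria are checked at which point, so that the rule on not randomising excluded patients agrees with the procedure. The same coordinator makes the same call, so the cost is a short delay before scheduling and a somewhat more selected population. That second cost is limited, because unreached and declining patients are already excluded.

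Moving the call does not remove the mode-switch exclusion. Patients who switch after randomisation should stay in their assigned arm for analysis. Asking beforehand about willingness to accept either mode is an option, at the price of a narrower population.

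**If queue randomisation is kept** to study attendance in unselected referrals, define the visit-completion analysis set as all randomised patients by assigned arm, including those who switch mode, decline or are not reached. State in advance how a visit attended in the other mode is counted. Report post-randomisation exclusions by arm with reasons, from the fields already recorded. This needs little new data collection, but the sponsor should confirm that the ethics approval covers using the records of patients who decline. It protects visit completion only; the survey outcomes would remain a comparison of those who entered and should be reported with that limitation.
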